- To define the most effective stimulation protocol by verifying if TBS in continuous mode (cTBS) produces better results at the behavioral level (based on scores of the neuropsychological assessment tests) than those obtainable with TBS in intermittent mode (iTBS).
- To investigate the neural mechanisms underlying neuroplasticity induced by the application of different treatment protocols, and to discover which of them is the basis for the greatest and most persistent clinical improvement. To evaluate the changes in neuroplasticity induced by the different therapeutic protocols and investigate the neural

correlates of the improvements obtained, this study will employ an innovative multimodal imaging technique: TMS-EEG co-registration.

OUTCOME MEASURES

To evaluate the efficacy of the treatment at a global level, the MMSE score will be the primary measure, while for a more in-depth evaluation of efficacy at the level of individual cognitive domains, the scores on the individual neuropsychological tests will be evaluated (primary objective and first secondary objective).

Neurophysiological indices collected through TMS-EEG co-registration will be used to evaluate any changes in neuroplasticity induced by the different therapeutic protocols and to identify a secondary marker of response to treatment. (second secondary objective).

[figure not shown]
STUDY DESIGN

The project involves the enrollment of 100 patients diagnosed with Alzheimer's disease, and 100 patients diagnosed with MCI (200 participants in total) according to the criteria in the patients section.

This is a randomized, non-pharmacological study with a double-blind certified medical device (neither the patient nor the clinician/researcher who will carry out the evaluations will be aware of the group to which the patient has been assigned).

In the screening phase, the patient's ability to provide consent to participate in the research will be assessed, according to the structure shown in Figure 1. In the event that the patient does not reach normal scores on the proposed tests, formal consent to participate in the research study will be required by the support administrator.

Figure 1. Screening for the evaluation of informed consent

[figure not shown]

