All patients included in the study will be randomly assigned to one of five different treatment protocols (20 patients diagnosed with AD and 20 patients diagnosed with MCI for each protocol), balanced using MMSE and age results so that the groups are homogeneous. In detail, the protocols are:

1. Combination of continuous TBS and cognitive training (cTBS + CT);
2. Combination of TBS in intermittent mode and cognitive training (iTBS + CT);
3. Isolated application of TBS in continuous mode (cTBS);
4. Isolated application of TBS in intermittent mode (iTBS);
5. Isolated application of cognitive training (with placebo TBS) (CT).

The treatment involves two main phases (Figure 1): 1) an intensive phase, lasting 2 weeks, with a daily frequency (5 times a week, for a total of 10 sessions); 2) a subsequent maintenance phase, lasting 5 weeks, with a biweekly frequency (2 times a week, for a total of 10 sessions).

Patients will undergo a clinical and neuropsychological evaluation and a neurophysiological evaluation before the start of treatment (baseline, t0), at the end of the intensive phase of treatment (t1), at the end of the maintenance phase (t2), and after 3 (t3) and 5 months (t4) from the start of treatment (Figure 2).

Figure 2. Study Design

Months Weeks	1				2				3				4				5				6				
	1	2	3	4	5	6	7	8	9	10	11	12	13	14	15	16	17	18	19	20	21	22	23	24	
Rehabilitative Treatment																									
Combined TBS +Cognitive Training (n. sessions)	5	5	2		2	2	2	2																	
Cognitive Training only (n. sessions)	5	5	2		2	2	2	2																	
TBS application only (n. sessions)	5	5	2		2	2	2	2																	
Evaluations																									
Clinical and Neuropsychological Evaluation	T0				T1				T2				T3								T4				
Neurophysiological Evaluation	T0				T1				T2				T3								T4				

 Intensive Treatment Phase
 Maintenance Phase

PATIENTS

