- 1) Intermittent theta burst stimulation (iTBS): this protocol consists of the administration of 600 pulses divided into blocks of 3 pulses at 50 Hz which are applied at 5 Hz (every 200 ms), alternating 2 s of stimulation with 8 s of pause (standard iTBS protocol originally proposed by Huang and Kandel 2005).
- 2) Continuous theta burst stimulation (cTBS): this protocol consists of the administration of 600 pulses divided into blocks of 3 pulses at 50 Hz that are applied at 5 Hz (every 200 ms) (standard cTBS protocol originally proposed by Huang and Kandel 2005).

In both stimulation protocols, the stimulation intensity will be equal to 80% of the motor threshold value at rest. As for the protocols that involve the application of sham/placebo stimulation, the rTMS will be administered by applying a piece of wood or plastic of about 30 mm in thickness to the coil, a distance that ensures that the magnetic pulse does not reach the cortex, and will be built so that it appears to be an integral part of the apparatus (Rossi et al., 2007). All stimulation parameters adopted in this study are in accordance with the safety guidelines for the application of rTMS (Rossi et al. 2009; Rossi et al. A Consensus Statement from the IFCN Workshop on "Present and Future of TMS: Safety and Ethical Guidelines ", Siena, October 17-20, 2018).

Cognitive rehabilitation protocol

For patients assigned to the protocol including the application of cognitive training (TBS + CT; CT), the training will be administered immediately following the application of rTMS (both in the real intermittent or continuous condition, and placebo) and will last 25 minutes. Cognitive training will be administered through dedicated software that uses an individualized adaptive methodology based on the participant's performance.

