The primary outcome for the calculation of the sample size was defined as the effect of the cTBS protocol and the iTBS protocol (both in combination with cognitive training) compared to the treatment involving the combination of cognitive training with TBS placebo and the one which involves only the TBS protocol applied in isolation, on the MMSE score obtained at the end of the treatment. Based on the results of a previous rTMS study on a sample of AD patients (Ahmed et al., 2012), we estimate that at the end of our treatment there will be an improvement in the MMSE score of at least 3 points (SD of change = 2.95) for protocols that involve the combination of cognitive training and real TBS, and of 0.2 points (SD of change = 2.7) for the treatment that involves the combination of cognitive training and placebo TBS.

Considering an alpha value of 0.05 and a power of 0.80, we estimate that the number of patients to be recruited should be 16 patients per group, increased to 20 per group to take into account a possible dropout rate of 20%.

Techniques provided for data processing

Behavioral and neurophysiological data will be analyzed by analysis of variance (ANOVA) and post-hoc comparisons (t-test, contrast analysis).

Statistical processing software

Data processing will be performed with BrainVision Analyzer, SPSS and/or Statistica software.

ETHICAL CONSIDERATIONS AND ASSESSMENT OF THE RISK/BENEFIT RATIO

Expected benefits

Based on the assumptions of the present project, patients who will receive the treatment that involves the combined application of rTMS and cognitive training should show a clinical response, based on the primary endpoints reported above, better than the patients assigned to the protocols in which rTMS and cognitive training are applied in isolation. The research also provides indirect scientific/cognitive benefits, in terms of advancing knowledge on the development of treatments with proven efficacy and on the mechanisms underlying Alzheimer's dementia.

Potential Risks

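### The protocol says patients will not know their group, but receipt of cognitive training is not masked, so the comparison of combination with TBS alone is not patient-blinded

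*Protocol*

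**What the plan says.** Study Design calls the trial double-blind and explains the term: "neither the patient nor the clinician/researcher who will carry out the evaluations will be aware of the group" assigned. The same section lists five arms. Arms 1 and 2 combine cTBS or iTBS with cognitive training. Arms 3 and 4 are "Isolated application of TBS in continuous mode (cTBS") and "Isolated application of TBS in intermittent mode (iTBS"). Arm 5 is "Isolated application of cognitive training (with placebo TBS) (CT").

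The Cognitive rehabilitation protocol section limits training to certain arms: "For patients assigned to the protocol including the application of cognitive training (TBS + CT; CT), the training will be administered" straight after stimulation, for 25 minutes. The Theta burst section describes a sham for the coil. No sham training or control activity is described for arms 3 and 4.

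The primary objective asks whether the combination does better than either method alone. The sample size section names both comparators for the MMSE: training with placebo TBS, and TBS alone. Under Expected benefits the protocol anticipates a response in the combined arms "better than the patients assigned to the protocols in which rTMS and cognitive training are applied in isolation".

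**The concern.** The blinding statement is about the assigned group, and what separates arm 1 from arm 3, and arm 2 from arm 4, is whether the patient does a 25-minute face-name task at each session. A patient cannot be unaware of that. The statement thus claims for all five arms a property that the design has only in part.

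The open part bears on the primary question. The MMSE is performed by the patient, so a blind evaluator does not remove differences in effort or expectation that come from knowing what one receives. If the trial is reported as double-blind throughout, a finding that the combination beats TBS alone will be read with the same confidence as the sham-controlled finding against arm 5, which it does not deserve.

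**Working it through.** **1. The plan's own figure.** The sample size section assumes changes of 3 and 0.2 points, with SDs of 2.95 and 2.7. The difference is 3 - 0.2 = 2.8 and the pooled SD is sqrt((2.95² + 2.7²)/2) = 2.828. With two-sided alpha 0.05 and power 0.80, n = 2 x (2.828 x (1.960 + 0.842)/2.8)² = 16.0 per group. Allowing for 20% dropout, 16/0.80 = 20. The stated 16 and 20 reproduce, and the blinding point does not change them.

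**2. What each arm lets the patient know.**

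| Arm | Stimulation | Training | Can the patient tell? |
|---|---|---|---|
| 1 | real cTBS | yes | knows they train; real or placebo masked by sham |
| 2 | real iTBS | yes | same |
| 3 | real cTBS | none | knows they do not train |
| 4 | real iTBS | none | knows they do not train |
| 5 | placebo TBS | yes | knows they train; real or placebo masked by sham |

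**3. Which contrasts are affected.** There are two comparators, and nothing masks the difference in one of them (TBS alone). Matched by TBS mode, the contrasts are 1 vs 5, 2 vs 5, 1 vs 3 and 2 vs 4; the last two of these four are open. If each combined arm is set against each TBS-alone arm, there are 2 x 2 = 4 open contrasts plus 2 masked ones, so 4 of 6. The protocol does not list its contrasts, so both counts are readings. Each arm enrols 20 AD + 20 MCI = 40 patients. The TBS-alone arms hold 2 x 40 = 80, and the open contrasts involve 4 x 40 = 160 of 200.

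**4. How different the sessions are.** Sessions: 10 intensive + 10 maintenance = 20. Training: 25 min x 20 = 500 min, or 8.3 h. Stimulation per session follows from the Theta burst section. For cTBS, 600/3 = 200 bursts x 0.2 s = 40 s. For iTBS, 30 pulses per 2-s train gives 600/30 = 20 trains, and 20 x 10 s - 8 s = 192 s. A few minutes at most against a further 25 minutes of tasks is not a difference that a patient could miss.

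**5. Direction of any bias.** Patients in arms 1 and 2 may expect more because they get an extra activity. But placebo TBS exists only in arm 5, so a patient who does not train could infer that the stimulation is real, which patients in arms 1 and 2 cannot. Expectation could therefore favour either side.

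**6. Illustration only.** The documents give no size for an expectancy bias and no SD for TBS alone. Assume no true difference, SD 2.95 on both sides (borrowed from the combined arms), 16 evaluable per arm and a two-sided 0.05 t-test (30 df, critical value 2.042). The standard error is 2.95 x sqrt(2/16) = 1.043, and the noncentrality is bias/1.043.

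| Assumed bias towards the combination (MMSE points) | Chance that the combination is declared better |
|---|---|
| +1.5 | 28.5% |
| +1.0 | 15.1% |
| +0.5 | 6.7% |
| 0 | 2.5% |
| -0.5 | 0.8% |
| -1.0 | 0.2% |
| -1.5 | below 0.1% |

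With AD and MCI pooled (32 evaluable per arm), +0.5, +1.0 and +1.5 give about 10%, 27% and 52%. The table shows only that the result depends on a quantity that the documents do not supply.

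**The case against.** The strongest defence is that the double-blind wording is attached to the device: stimulation is what the sham masks, the arms are listed openly, and training can hardly be hidden from the person doing it. What stands is that masking of stimulation is not impeached. But the parenthesis defines blinding as unawareness of the group, so if only the device was meant, the sentence needs correcting.

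Several stronger readings are tempting and lack support:

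- *Patients are blind only within arms 1, 2 and 5.* Nothing shows that patients learn whether they receive cTBS or iTBS. The calculated durations differ (40 s and 192 s), but each patient receives one mode and the documents do not say that durations are disclosed. So 1 vs 2 and 3 vs 4, which serve the first secondary objective, should not be declared open.
- *The design favours the combination by a known amount.* The percentages for positive bias alone suggest this, but the bias values are assumed and the direction is unknown.
- *The 500 minutes of extra contact are bias.* If the contrast is defined as the effect of adding training, contact is part of that effect. Only expectancy from knowing the allocation could count as bias, and the documents do not allow it to be separated out.
- *Evaluators are unblinded too.* Patients could disclose what they receive, but the protocol's promise for evaluators is separate and nothing contradicts it.

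How much patients know of the other arms depends on consent text that is not available. The protocol says only that they receive explicit information about the nature of the project. That affects how strong any expectancy would be, but not whether patients know that they train.

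**Conclusion.** The point holds for patient blinding to training. The statement in Study Design cannot be true for arms 3 and 4 against arms 1 and 2, and so not for one of the two primary comparators (two of four mode-matched contrasts, 160 of 200 patients). This rests on the arm list and the training rule, with the one assumption that no control activity exists beyond what the protocol describes. The effect on the MMSE comparison is of unknown size and direction, and no inflation of false positives can be claimed from the documents. The sample size, the sham for real versus placebo TBS among the training arms, the masking of TBS mode and the evaluator blinding are all untouched. The statement should be corrected; the design need not change.

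**What to change.** Replace the blinding statement in Study Design with: *Evaluators are blind to group in all comparisons. Patients are blind to stimulation type only (real versus placebo TBS among the arms with training, and cTBS versus iTBS mode). Receipt of cognitive training is not masked.*

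Then add that:

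- arms 1 and 2 vs 5 are the patient-blinded part of the primary comparison;
- arms 1 vs 3 and 2 vs 4 are open to the patient and estimate the effect of adding training, including its contact time (25 min x 20 sessions);
- any conclusion that the combination is better than TBS alone is limited to that effect, here and under Expected benefits.

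The change is to wording only: no new arm, procedure or patients. The price is a less favourable description of blinding and a narrower claim against TBS alone.

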- Ongoing treatments with drugs that contain/require intake of the following substances (Rossi et al. 2009): imipramine, amitriptyline, doxepin, nortriptyline, maprotiline, chlorpromazine, clozapine, foscarnet, ganciclovir, ritonavir, amphetamines, cocaine, (MDMA, ecstasy), phencyclidine (PCP, angel dust), gamma-hydroxybutyrate acid (GHB), theophylline.
- Presence of cardiac pacemakers, electronic prostheses, biostimulators, metal inserts or electrodes implanted in the brain or skull or spine.
- Non-fulfillment of the inclusion criteria for TMS (absolute exclusion criteria) (Rossi et al., 2009), which in detail are:
 - presence of cardiac pace-makers, artificial heart valve and/or biostimulators;
 - presence of hearing aids located in the middle ear;
 - presence of metal inserts in the head and/or shoulders;

METHODS AND PROCEDURES

The materials and methods of investigation proposed will be the following:

- Administration of rTMS in theta burst mode (TBS - intermittent and continuous)
- Administration of computerized cognitive training
- Administration of a battery of neuropsychological tests
- Administration of questionnaires and scales
- Recording of the electroencephalogram (EEG)
- Combination of EEG recording with single-pulse TMS administration (TMS-EEG)

Theta burst brain stimulation protocol

rTMS will be applied using a magnetic stimulator (Magstim Super Rapid2 of which the technical data sheet, declaration of conformity and registration number in the Ministry of Health database is attached) connected to a 70 mm eight-shaped coil that generates ~ 2 Tesla maximum. Once the stimulation intensity has been defined (equal to the subjective motor threshold, i.e. at an intensity equal to 100% of the motor threshold previously determined by a surface electromyographic recording of the first dorsal interosseous of the hand), the coil will be positioned on the target area and stabilized with a mechanical support. The TBS will be applied to the left dorsolateral prefrontal cortex (DLPFC left) and the coil will be positioned at the position of the reference electrode (F3) according to the 10-20 International System.

Different TBS stimulation protocols will be applied:

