The psychological evaluation involves the administration of a scale that evaluates depressive symptoms in the elderly (*Geriatric Depression Scale, GDS*), a questionnaire on the quality of life and identification of deficits for the patient and for the caregiver (*QID*), a scale that evaluates awareness of deficits and disease (*Clinical Insight Rating Scale, CIRS*) and a scale to evaluate the patient's perception of empathy (*Jefferson Scale*).

Neurophysiological evaluation

Patients will undergo EEG recording and TMS-EEG co-registration before the start of treatment (t0), at the end of the intensive treatment phase (t1), at the end of the maintenance phase (t2), and after 3 (t3) and 5 months (t4) from the start of treatment (Figure 1).

The EEG will be acquired from 64 sintered Ag / AgCl electrodes placed on the scalp in accordance with the international 10-20 system, through an EEG acquisition system compatible with TMS. The EEG signal will be acquired with a high-pass filter at 0.01 Hz, a low-pass filter at 1000 Hz and with a sampling frequency of 5000 Hz. The impedance of the electrodes will be kept

below 5 kΩ. The TMS-EEG co-registration will consist of the administration of 120 pulses on the target area stimulated in the application phase of the protocol (right DLPFC or left DLPFC) at an intensity equal to 110% of the motor threshold at rest with a random frequency between 0.2- 0.4 Hz. The analysis of the data recorded by the combination of TMS-EEG will allow an in-depth evaluation of the modulations of cortical activity induced by the different treatment protocols and, in particular, will allow the investigation of cortical excitability and inhibition, cortico-cortical connectivity, and the intrinsic ability of the stimulated areas to generate oscillatory activity (Chung et al. 2015). This method will be able to provide a unique measure of local cortical activity and effective cortical-cortical connectivity (Bortolotto et al. 2015). Specifically, the analyses will focus on:

- 1) Potentials Evoked by TMS (TMS evoked potentials - TEP): TEPs represent the changes induced during the state of excitability/inhibition in the brain circuits following the TMS impulse. The amplitude of the TEPs will be used as a marker of cortical excitability. The analysis of TEP data will be performed using the measurements of the average amplitude values detected in successive time windows.

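### The theta burst section gives two different treatment intensities: 100% of an unspecified motor threshold, and 80% of the resting motor threshold

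*Protocol*

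**What the plan says.** Both statements stand in the Protocol, Methods and Procedures, under the heading Theta burst brain stimulation protocol.

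- **Opening paragraph.** A sentence on setting up the coil begins "Once the stimulation intensity has been defined (equal to the subjective motor threshold" and then gives the same value as a figure: "at an intensity equal to 100% of the motor threshold previously determined by a surface electromyographic recording". It also says how the threshold is found, by "surface electromyographic recording of the first dorsal interosseous of the hand". It does not say whether the threshold is resting or active.
- **After the descriptions of iTBS and cTBS.** "In both stimulation protocols, the stimulation intensity will be equal to 80% of the motor threshold value at rest".

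One other stimulation intensity appears in the Protocol. Under Neurophysiological evaluation, the single pulses for TMS-EEG are given "at an intensity equal to 110% of the motor threshold at rest".

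**The concern.** Intensity is a basic dose parameter of brain stimulation, and the same section sets it at two values. Neither sentence refers to the other, and no rule of precedence is given. An operator who sets up from the opening paragraph and one who sets up from the later sentence could use different intensities, each with a sentence of the protocol in support. A reader wishing to reproduce the treatment would not know which to use.

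What is at stake is the definition of the intervention, not the statistics. The ambiguity reaches every arm with active stimulation: cTBS and iTBS, each with and without cognitive training. If the setting varied between operators or over time, the treatment under test would be a mixture that the protocol does not describe.

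**Working it through.** The protocol derives no figure on this point, so the check compares the statements and takes one ratio.

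**1. Do both statements concern treatment?** Yes. The set-up sentence goes on to place the coil on the target, and the next sentence reads "The TBS will be applied to the left dorsolateral prefrontal cortex (DLPFC left". The list of methods names theta burst as the only form of repetitive stimulation, in its intermittent and continuous modes. The later sentence covers both modes, so no third mode is left for the 100% to describe.

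**2. Could the 100% be the TMS-EEG setting?** No. That is a separate assessment procedure with its own intensity, 110% of resting threshold.

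**3. Could the opening paragraph only be describing how the threshold is measured?** Not as worded. It makes the stimulation intensity equal to the threshold, once in words and once as 100%, so a single mistyped digit is an unlikely explanation. If only measurement was meant, the sentence still needs correcting.

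**4. How large is the difference?** Write R for a patient's resting threshold and X for the threshold meant in the opening paragraph.

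| Statement | Intensity |
|---|---|
| Opening paragraph | 1.00 × X |
| After iTBS and cTBS | 0.80 × R |

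- If X = R, the ratio is 100/80 = 1.25, so the first intensity is 25% above the second. Equivalently, 80/100 = 0.80, so the second is 20% below the first. The ratio is the same for every patient.
- If X is another threshold, the ratio is X / (0.80 × R), and the two statements agree only if X = 0.80 × R. The protocol names no active threshold and gives no conversion between thresholds, so this ratio cannot be computed and agreement cannot be assumed.

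**5. How much of the trial does it touch?** Study Design plans 20 patients with AD and 20 with MCI per arm. Four active-stimulation arms × 40 = 160 of the 200 planned patients, each with 10 intensive + 10 maintenance = 20 sessions.

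**6. What is not in conflict?** Both modes use 600 pulses, and each burst pattern is stated once. The sample-size calculation does not use intensity, so its inputs and result stand.

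**The case against.** The strongest reply is that the practical ambiguity is small. The 100% sits in a parenthesis within a sentence about placing the coil. The 80% is a direct instruction that comes later, covers both modes and names the threshold type. On an ordinary reading the specific instruction governs, and an operator using 100% of resting threshold would be breaching it. The 100% may be leftover wording: Neurophysiological evaluation also mentions a right-sided target, whereas the theta burst section fixes only the left. The 25% is conditional on the threshold type, and nothing shows that operators would in fact diverge.

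Most of this stands. It supports 80% of resting threshold as the likely intent, and divergence between operators is a possibility rather than a demonstrated outcome. It is also right that variation in intensity unrelated to arm would blur the intervention and might dilute effects, but would not in itself invalidate the randomised comparisons. None of it removes the conflict. Likely intent has to be inferred, no sentence sets the order of precedence, and the leftover-text explanation concedes that the parenthesis is wrong as it stands.

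**Conclusion.** The inconsistency is real and minor. One section gives two treatment intensities for the same stimulation, and no text reconciles them. The difference is 25% (or 20%, taken the other way) on the assumption that both statements mean the resting threshold. Without that assumption its size cannot be derived from the document. The more specific sentence makes 80% of resting threshold the probable intent. Sample size, power, error rate and planned analysis are unaffected, and the randomised comparisons remain valid if one setting is used throughout. Neither value is criticised here as a choice of dose.

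**What to change.** State one intensity together with its threshold type.

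- **Default.** Delete the 100% statement from the parenthesis, including the words that equate the intensity with the threshold, so that 80% of the resting motor threshold governs. Keep the description of surface electromyography of the first dorsal interosseous, which appears nowhere else in the Protocol, and add there that the threshold is measured at rest.
- **If 100% was intended.** Correct the later sentence instead and name the threshold.
- **If recruitment has started.** Establish from stimulator or session records, where they exist, which setting was delivered. The Protocol does not describe such records.

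The cost is the correction of one parenthesis (or one sentence), plus a check of records if patients have already been treated. No extra patients or procedures are needed.

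### Patient blinding in the placebo arm is at risk and unchecked, and the placebo has no stated pattern although it controls two modes lasting 40 s and 192 s

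*Protocol*

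**What the plan says.** The Study Design section of the protocol declares the trial double-blind: "neither the patient nor the clinician/researcher who will carry out the evaluations will be aware of the group". It lists five arms of 20 AD and 20 MCI patients each. Only arm 5, cognitive training (CT), has a placebo. It is therefore the only placebo control for both combination arms, cTBS+CT and iTBS+CT.

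The section on the theta burst protocol defines the placebo: "the rTMS will be administered by applying a piece of wood or plastic of about 30 mm in thickness to the coil". Its thickness is described as "a distance that ensures that the magnetic pulse does not reach the cortex". As to its look, the section promises only that the piece "will be built so that it appears to be an integral part of the apparatus". It says nothing on scalp sensation, and does not say whether the placebo follows the continuous or the intermittent pattern, or how long it lasts. Both real modes deliver 600 pulses in groups of three, five groups per second; the intermittent mode does so "alternating 2 s of stimulation with 8 s of pause".

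The section on neurophysiological evaluation applies to all patients, at t0 and at every later assessment: "The TMS-EEG co-registration will consist of the administration of 120 pulses on the target area stimulated in the application phase of the protocol". These are single pulses at 110% of resting motor threshold and 0.2 to 0.4 Hz.

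The sample size section assumes MMSE gains of 3 points (SD 2.95) for the combination arms and 0.2 points (SD 2.7) for CT with placebo TBS.

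**The concern.** There are two separate weaknesses in the one comparison for which a placebo exists.

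First, the placebo has to convince patients who have already felt real TMS. A patient in arm 5 meets real pulses over the target area before the first placebo session, and meets them again at t1, after ten placebo sessions and before the next ten. The placebo is described by how it looks and by what it keeps from the cortex, not by how it feels. The placebo description and the TMS-EEG description do not refer to each other, and the protocol plans no question to patients that would show whether blinding held.

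Second, one placebo arm stands against two procedures of very different length, and its own pattern is left open. If a single pattern is used, at least one of the two combination arms differs from its control in session length and rhythm as well as in real stimulation.

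MMSE is a performance test, and training follows stimulation directly, so a patient's expectation could affect both. A blinded assessor does not remove that. Any expectation effect would be counted as a stimulation effect in the contrast on which the trial is sized.

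**Working it through.** **Session length** (inputs from the theta burst section)

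- Bursts in either mode: 600 / 3 = 200.
- cTBS: 200 / 5 per second = 40 s without a break.
- iTBS: 2 s × 5 bursts = 10 bursts per train; 200 / 10 = 20 trains; 20 × 2 s + 19 × 8 s = 192 s.
- Ratio: 192 / 40 = 4.8.
- Over 20 sessions (10 intensive and 10 maintenance): 20 × 40 s = 800 s, about 13 minutes; 20 × 192 s = 3,840 s = 64 minutes.

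**Real TMS met by arm 5** (inputs from the neurophysiological section)

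- Length of one TMS-EEG recording: 120 / 0.4 = 300 s to 120 / 0.2 = 600 s, that is 5 to 10 minutes of real single pulses per visit.
- Order for an arm 5 patient: real pulses at t0, 10 placebo sessions, real pulses at t1, 10 placebo sessions, real pulses at t2.

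**The protocol's own sample size**

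- Difference: 3 − 0.2 = 2.8. Sum of variances: 2.95² + 2.7² = 8.7025 + 7.29 = 15.9925.
- n = (1.96 + 0.8416)² × 15.9925 / 2.8² = 7.849 × 15.9925 / 7.84 = 16.01 per group (two-sided 5%, normal approximation; the protocol does not state the sidedness). Power at 16 is 0.7997, so the stated 16 is reproduced up to rounding.
- Dropout: 16 / 0.80 = 20, as stated.

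**What an expectation bias would do to the error rate**

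- SE of the difference with 16 per group: √(15.9925 / 16) = 1.00 MMSE point.
- With no true effect and a bias b, the two-sided rejection rate is Φ(−1.96 + b/SE) + Φ(−1.96 − b/SE).

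| Assumed bias (MMSE points) | Rejection rate |
|---|---|
| 0 | 5.0% |
| 0.5 | 7.9% |
| 1.0 | 17.0% |

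The protocol gives no figure for such a bias. The non-zero rows are illustrations.

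**The case against.** Several stronger readings are tempting, and the document does not support them.

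- **The TMS-EEG visits use the same coil, so the spacer would be visible by comparison.** The 70 mm coil is named for the treatment stimulation only; no coil is named for TMS-EEG. The protocol also addresses appearance explicitly.
- **The 40 s and 192 s sessions reveal the condition.** They do not. Arms are parallel, each patient meets one mode, and nothing says that patients are told the durations. The difference is a matching problem, not a route to unmasking.
- **The placebo cannot match both modes.** The pattern is unspecified, and a split between the two patterns within arm 5 is open. What holds is that any single pattern fails to match one of them.
- **Arm 5 patients can recognise placebo.** This is not shown. TMS-EEG gives slow single pulses at 110% of threshold during a 64-electrode recording; treatment gives fast bursts at another intensity. Patients on real TBS will also find treatment different from t0, so noticing a difference does not identify placebo.

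It is also fair to say that the cited placebo-device paper cannot be checked here and may cover sensation, that the consent pages are not available and so what patients know about a placebo is unknown, that the protocol keeps allocation from patients even after the study, and that a blinded assessor administers the MMSE.

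These points limit the claim to a risk. They do not remove it. Patients in arm 5 still have a reference for real TMS that the placebo is not described as reproducing, nothing planned would show whether blinding held, and the placebo's pattern is still open.

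**Conclusion.** The point holds as a risk to patient blinding in arm 5 that the design neither secures nor checks, and, separately, as an unspecified placebo procedure serving two unlike modes. It touches 40 of 200 patients, who form the control in the contrast whose assumed effects size the trial. The 4.8-fold difference in session length follows from the protocol's own parameters. The error rates of about 8% and 17% rest entirely on the assumed biases of 0.5 and 1.0 point, with 16 per group, the protocol's SDs and a two-sided normal test; with no bias the rate is 5%. Whether patients would in fact tell placebo from real stimulation cannot be determined from the document. The change is worth making before enrolment, but the trial is not invalid without it.

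**What to change.** 1. **State the placebo's pattern and split it.** Within arm 5, give the placebo in the cTBS pattern to half and in the iTBS pattern to half of the patients in each diagnosis (10 + 10). When both combination arms are pooled against arm 5, the control then has the same mix of patterns. The cost is that only half of arm 5 matches each single mode exactly. Restricting one mode's contrast to its matched half, with 20% dropout (16 against 8), gives SE = √(2.95²/16 + 2.7²/8) = 1.21 instead of 1.00, and power of about 64% for 2.8 points (2.8 / 1.206 − 1.96 = 0.36). The whole of arm 5 should therefore stay in the main contrast, with the matched half as a supporting look.
2. **Check the blinding.** Ask patients in arms 1, 2 and 5 at t1 and t2 whether they think they received real or placebo stimulation, and report the answers by arm beside the primary contrast. The cost is one question at two existing visits. Guesses can partly reflect perceived benefit, so they qualify the result and do not correct it.
3. **Temper the statement.** Unless the placebo device is shown to match scalp sensation, say that patient blinding to placebo is unverified.
4. **Reconcile two contradictions in the same sections.** The target is left DLPFC only in the theta burst section but right or left DLPFC in the neurophysiological section. Within the theta burst section, stimulation intensity is given as 100% of motor threshold in one place and 80% in another. The sponsor must settle both.

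No extra patients, visits or assessments are needed.
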